We will add apremilast to their treatment regimen according to the approved dosage for psoriasis and psoriatic arthritis: 10 mg orally one time on day 1, 10 mg orally twice daily on day 2, 10 mg orally in

AM and 20 mg orally in PM on day 3, 20 mg orally twice daily on day 4, 20 mg orally in AM and 30 mg orally in PM on day 5, then 30 mg orally twice daily thereafter.

7. Brief Study Synopsis: With limited treatment options available for dermatomyositis, we hypothesize that apremilast, a phosphodiesterase-4 (PDE-4) inhibitor, is a safe and efficacious add-on treatment in patients with recalcitrant cutaneous dermatomyositis.

The study will investigate the efficacy, safety and toxicity of apremilast given at 30 mg twice daily to patients with recalcitrant cutaneous dermatomyositis. Clinical response will be assessed at 1 and 3 months. Patients will also be evaluated for durability of their response for up to 6 months.

Treatment will be monitored with frequent clinical visits (0, 1, 3 and 6 months) and blood tests (CBC, CMP, CK, aldolase). Treatment will be discontinued at disease progression or unacceptable adverse events. Disease progression is defined as a 4 points increase in CDASI score, worsening of muscle disease by MMT-8 score and 5 points increase in DLQI.

5 mm skin biopsies from lesional skin will be performed before treatment with apremilast and after 3 months of treatment for gene expression profiling and confirmatory immunohistochemical stains.

8. Inclusion Criteria:

- Must understand the risks and the benefits/purpose of the study and provide signed and dated informed consent.
- Must be 18 years at time of signing the informed consent form.
- Willing to participate in all required evaluations and procedures in the study including the ability to swallow pills without difficulty.
- Patients must have a diagnosis of DM based upon the characteristic cutaneous findings proposed by Sontheimer^[6] and/or a skin biopsy consistent with DM.
- Patients must be candidate for systemic therapy for their DM skin disease defined by inadequate response to aggressive sun protection along with the use of potent topical corticosteroids and/or immunomodulators.
- Patients with a diagnosis of dermatomyositis on steroid-sparing agent and/or systemic steroids (maximum dose of prednisone 1mg/Kg) and still having cutaneous disease activity of at least 5 on the CDASI scale.

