Photograph of skin rash will be taken at months 0,1 and 3 and compared to baseline.

2. Secondary Objective(s) Description

To determine the durability of responses for up to 6 months on apremilast for responders at 3 months. The durability of responses includes partial and complete response durability. The durability of response will be measured using the CDASI at 6 months minus CDASI at 3 months. Complete response durability is defined as zero or minus difference between CDASI score at 6 months and CDASI score at 3 months. Partial response is defined as >4 points difference between CDASI score at 6 months and CDASI score at 3 months.

We will assess the response of all patients at 6 months to identify possible delayed response. Complete response is defined by a CDASI score of zero at 6 months. Partial response is defined by a decrease of CDASI score of at least 4 points at 6 months compared to baseline. Calculation is performed as the CDASI score at 6 month(s) minus the score at baseline.

Photograph of patient's rash will be taken at 6 months and compared to 3 months and baseline.

To determine the safety and toxicity of apremilast when administered at 30 mg twice daily in patients with dermatomyositis. The safety assessment will include the assessment of adverse events, serious adverse events, laboratory testing and physical examination.

An additional secondary endpoint will be to determine if patients who experience remission of their disease can be maintained on apremilast as monotherapy.

To determine the patient quality of life using the Dermatology Life Quality Index (DLQI)^[15] at baseline, 1, 3 and 6 months.

Patient will be assessed 1 month after discontinuing apremilast (follow up visit) to assess change in response post discontinuation of apremilast. Patients will be examined and, CDASI, MMT-8 and DLQI will be performed. Photograph of patient's rash will be taken. CBC, CMP, CK, aldolase and urine pregnancy test will be performed.

3. Exploratory Objectives:

We will measure muscle enzymes (creatin kinase (CK) and aldolase) at 0, 1, 3, and 6 month(s) of apremilast in patients with muscle disease.

We will assess disease activity using the manual muscle testing-8 (MMT-8) in patients with muscle disease.^[16]

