Skin biopsies from lesional skin will be performed before treatment with apremilast and after 3 months of treatment for gene expression profiling and IHC stain. IHC will be performed on the protein product of the genes showing the largest fold change from the RNA-sequencing.

All investigators (PI and Sub-Is) will be trained on how to screen the patients per the MMT-8 score tool.

V. STUDY ENROLLMENT AND TIMELINES

1. # of Patients Expected to Enroll: 10

2. Date of planned FSI: 04/02/2018

3. Date of planned LSI: 11/01/2018

4. Date of planned LSO: 05/01/2019

5. Patient treatment duration (# months): 6 months

6. Is an interim Analysis Planned? Yes

7. Date on planned Interim Analysis: 03/01/2019

8. Date of planned final report: 06/03/2019

9. Are patients reported outcomes measured: Yes

VI. STATISTICAL PLAN:

Results of the study will be analyzed using descriptive statistics:

- Proportion of patients with complete ORR at 1,3 months
- Proportion of patients with partial ORR at 1,3 months
- Proportion of patients with complete durability response at 6 months for the 3 months responders
- Proportion of patients with partial durability response at 6 months for the 3 months responders
- Proportion of patients with complete response at 6 months
- Proportion of patients with partial response at 6 months
- Mean change from baseline in muscle enzymes (CK and aldolase in patients with muscle disease)
- MMT-8 change will be calculated as mean change from baseline at 1,3 and 6 months
- DLQI change will be calculated by identifying the proportion of patients with minimal clinically important difference of at least 5 points.

Missing data will be handled using the last observation carried forward approach (LOCF).

GEP will be analyzed using inferential statistics with a False Discovery Rate (FDR) of < 0.05 .

VII. INFORMED CONSENT:

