XII. BUDGET

1.Currency Type: US Dollars.

3. Total requested Amount from Celgene: \$ 40,000

Schedule of Events

Procedure	Screening phase	Baseline (Day 0)	Month 1	Month 3	Month 6	Follow up visits
Informed Consent	X					
Demography	X					
Medical History	X	X				
Inclusion/Exclusion Criteria	X	X				
Photograph		X	X	X	X	
Hematology	X		X	X	X	X
Serum Chemistry	X		X	X	X	X
Muscle enzymes (CK, aldolase)	X		X	X	X	X
T-spot	X					
Skin biopsy		X		X		
Safety Assessments						
Adverse Events		X	X	X	X	X
Vital Signs	X	X	X	X	X	X
Physical Examination	X	X	X	X	X	X
Weight	X	X	X	X	X	X
Urine Pregnancy test (every month)	X	X	X	X	X	X
Contraception Education	X	X	X	X	X	X
Efficacy Assessments						
CDASI	X	X	X	X	X	X
MMT-8		X	X	X	X	X
DLQI		X	X	X	X	X
PHQ-2	X	X	X	X	X	X
Dispense ID (every month)		X	X	X	X	

Timeframe between screening phase and day 0 of the study should not exceed 1 month.

I. REFERENCES

- [6] Sontheimer RD. Dermatomyositis: an overview of recent progress with emphasis on dermatologic aspects. *Dermatologic clinics* 2002; 20:387-408.

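### LOCF scores a month-3 responder with no later CDASI as complete durable, without any evidence of durability

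*Combined protocol and SAP*

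**What the plan says.** Section VI (Statistical Plan) has one rule for missing data: "Missing data will be handled using the last observation carried forward approach (LOCF". It exempts no endpoint, makes no distinction by reason for missingness and plans no sensitivity analysis. The same section lists, as a descriptive result, "Proportion of patients with complete durability response at 6 months for the 3 months responders".

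Section IV.2 (Secondary Objectives) sets the measure: "The durability of response will be measured using the CDASI at 6 months minus CDASI at 3 months". It then gives the threshold: "Complete response durability is defined as zero or minus difference between CDASI score at 6 months and CDASI score at 3 months".

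On timing, the Brief Study Synopsis says "Treatment will be monitored with frequent clinical visits (0, 1, 3 and 6 months"; the Schedule of Events agrees and adds a column headed "Follow up visits". Two other sources of a CDASI after month 3 are possible. One is a score taken to establish progression, since the Synopsis says "Disease progression is defined as a 4 points increase in CDASI score" (together with muscle and DLQI criteria). The other is the visit in Section IV.2: "Patient will be assessed 1 month after discontinuing apremilast (follow up visit) to assess change in response post discontinuation of apremilast".

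**The concern.** Durability is itself the change over the interval in which the score is missing. Carrying the month-3 score to month 6 sets that change to zero, and zero is inside the definition of success, so the imputation supplies the outcome. A responder who is never seen again is counted as complete durable, whereas one who is seen at month 6 and is 1 point worse is not.

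Missingness may also be related to outcome. The Synopsis stops treatment at progression or unacceptable adverse events, and Section IX lists adverse events, lack of effect and loss to follow-up among the reasons for withdrawal. Nothing in the plan says that such a patient counts as not durable. With 10 patients planned (Section V), the durability denominator is at most 10, so one or two such patients can move the reported proportion visibly, and the reader would not be told how many scores were imputed.

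**Working it through.** The plan gives no durability, dropout or response figure, so there is nothing to reproduce. The check applies the plan's rules directly and then uses assumed counts.

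**Step 1: the rule for one patient.** Let D = CDASI(6) − CDASI(3) (Section IV.2). If the month-3 score is observed and nothing follows, LOCF sets CDASI(6) = CDASI(3), so D = 0. This meets the complete-durability threshold (D ≤ 0) and not the partial one (a difference above 4 points). The result is the same for every baseline score and every month-3 score that qualifies as a response.

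**Step 2: effect on the proportion.** Let R = month-3 responders, all with an observed month-3 score; k = those with no later CDASI; x = complete durable among the R − k with a month-6 score; t = those of the k who truly stayed durable.

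- LOCF: (x + k)/R
- Missing counted as not durable: x/R
- Observed cases: x/(R − k)
- True value: (x + t)/R
- LOCF error: (k − t)/R, between 0 and +k/R
- Missing-as-not-durable error: −t/R, between −k/R and 0

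**Step 3: size per patient, against missing-as-not-durable.** With k = 1 the difference is 1/R: 1/4 = 25 points, 1/6 = 17 points, 1/10 = 10 points.

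**Step 4: size against observed cases.** The difference is (x + k)/R − x/(R − k) = k(R − k − x)/[R(R − k)]. It is 0 when every completer is durable (x = R − k). For R = 4, k = 1, x = 2 it is 1/12 = 8 points (75% against 67%).

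**Step 5: one worked example (assumed R = 6, k = 2, x = 2).** LOCF gives 4/6 = 67%, observed cases 2/4 = 50%, missing-as-not-durable 2/6 = 33%.

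| t | True value | LOCF error | Missing-as-not-durable error |
|---|---|---|---|
| 0 | 2/6 = 33% | +33 points | 0 |
| 1 | 3/6 = 50% | +17 points | −17 points |
| 2 | 4/6 = 67% | 0 | −33 points |

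**Step 6: the off-drug score.** The plan does not say whether the CDASI taken 1 month after stopping may stand in for month 6. A patient who stops at month 5 has that visit at month 6. If the 2 patients in Step 5 had instead stopped early and their follow-up CDASI were above the month-3 score, durability would be 2/6 = 33% if that score is carried to month 6 and 4/6 = 67% if it is not.

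**Step 7: a missing month-3 score.** Assume 4 observed month-3 responders, 2 of them durable, and one further patient last scored at month 1.

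- If that patient was a month-1 responder, LOCF makes the patient a month-3 responder with D = 0: 3/5 = 60%, against 2/4 = 50% among observed month-3 responders.
- If that patient was a month-1 non-responder, LOCF removes the patient from the denominator: 2/4 = 50%. Had the patient responded by month 3 and stayed durable, the true value would be 3/5 = 60%.

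**Step 8: response at 6 months.** Section IV.2 also assesses all patients at month 6 against baseline. With CDASI(6) = CDASI(3), the change from baseline is unchanged, so a month-3 responder with no later score is a 6-month responder as well.

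**The case against.** The affected group is narrow. A patient who stops apremilast but stays in contact is due a CDASI one month later, and progression is itself partly a CDASI finding, so the mechanism applies mainly to patients who leave with no further assessment. This stands: patients with a later CDASI are outside the point, and no document figure supports the assumed counts.

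The largest differences depend on the comparator. Against observed cases the Step 5 shift is 17 points and not 33, and it can be zero. This also stands, and the comparator should always be named.

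Counting missing as not durable is biased too, by up to the same amount in the other direction. That is correct, and it is why the alternatives need to be reported together. It does not rescue LOCF as the only analysis, because LOCF credits success to patients who were not assessed.

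Part of the contrast with an observed 1-point worsening comes from the definitions: rises of 1 to 4 points fit neither category, and the partial threshold has no stated direction. That is a separate matter, and a missing-data rule will not settle it.

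A reader might infer that LOCF gives an upper bound for the whole durability endpoint. It does not: a carried month-1 non-response can put LOCF below what the data allow (Step 7, 50% against 60%). A reader might also infer that the primary month-3 response rate is biased upward. The documents do not support that: a carried month-1 score can err in either direction there.

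**Conclusion.** The point holds for month-3 responders with an observed month-3 score and no later CDASI. They are scored complete durable by rule, and for them the error is zero or upward, (k − t)/R. Each adds 1/R compared with counting missing as not durable, and less compared with observed cases. The same carry-forward makes them responders in the separate 6-month analysis.

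The documents do not show that the reported durability will be inflated, or by how much: R, k and t are unknown, and with complete month-6 follow-up there is no effect. The endpoint is secondary and descriptive, with no test, error rate or sample size attached. Severity is minor to moderate.

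**What to change.** Amend the missing-data paragraph of Section VI as follows.

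- Exempt durability and 6-month response from LOCF.
- Durability denominator: patients with an observed month-3 CDASI that meets the response definition. This avoids imputing a patient as a month-3 responder and then counting the same patient as a durability failure.
- A missing month-6 CDASI counts as not shown durable (neither complete nor partial) and as non-response at 6 months, so that the two tables agree.
- Report the number missing beside each proportion, with LOCF and observed-case results as sensitivity analyses.
- State that the post-discontinuation CDASI is not substituted for the month-6 on-treatment score. Section IV.2 frames durability as response on apremilast.
- For the month-3 ORR, LOCF may stay; report the number imputed and add missing-as-non-response as a sensitivity analysis.

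The cost is one paragraph and no new data collection. The main durability figure becomes conservative: it understates durability by t/R, up to 33 points in the example with R = 6 and k = 2, and the sensitivity analyses show that range. The durability denominator may also differ from the number of responders in the LOCF-based ORR, and the report should say so where it does. The rule should be fixed before results are seen, because a later choice among 67%, 50% and 33% would be post hoc.

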RNA extracted from skin biopsies collected before and after *in vivo* treatment with apremilast (as detailed above) will be subjected to RNA sequencing. Illumina strand-specific TruSeq libraries will be prepared from the polyA selected RNA and subjected to 1x100 base sequencing on an Illumina HiSeq2500 machine. The number of samples proposed here (10 samples before treatment and 10 samples after treatment) is expected to yield sufficient statistical power for this approach; smaller numbers have been used in similar approaches to investigate drugs' mechanism of action (usually three samples).^[7-9]

RNA-seq analysis will be performed in conjunction with the Tulane Cancer Crusaders Next Generation Sequence Analysis Core (Tulane Cancer Center - <https://tulane.edu/som/cancer/research/core-facilities/cancer-crusaders/>). Gene and isoform expression will be determined using RSEM^[10] and differential expression will be analyzed using EB-seq.^[11] Genes that are identified as differentially expressed between the two groups with a False Discovery Rate (FDR) of < 0.05 will be subjected to analysis by *Ingenuity* (IPA, Redwood City, CA). This analysis will group the identified genes into specific pathways, cell types, or disease process. A similar approach will be conducted using *Gene Set Enrichment Analysis (GSEA)*. These experiments and GEP analysis will be performed in conjunction with our collaborator's ([name]) lab, given his extensive experience in this field.^[12, 13]

b. Protein analysis

Information identified by Ingenuity or GSEA (signaling pathways, regulatory molecules, etc...) will be verified using IHC staining on select samples.

IV. OBJECTIVES AND ENDPOINTS

1.Primary Objective Description

To determine the overall response rate (ORR) of apremilast in cutaneous disease of patients with recalcitrant dermatomyositis at 3 months.

The ORR will be measured using the Cutaneous Dermatomyositis Activity and Severity Index (CDASI) at months 0, 1, and 3.

CDASI is a validated tool to measure skin disease activity in dermatomyositis.^[14] ORR includes partial and complete responses. Complete response is defined by a CDASI score of zero. Partial response is defined by a decrease of CDASI score of at least 4 points. Calculation is performed as the CDASI score at 1, and 3 month(s) minus the score at baseline.

All investigators (PI and Sub-Is) will be trained on how to screen the patients per the CDASI score tool.

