If the sequela of an overdose is an SAE, then the sequela must be reported on an SAE report form. The overdose resulting in the SAE should be identified as the cause of the event on the SAE report form but should not be reported as an SAE itself.

In the event of an overdose, the patient should be monitored as appropriate and should receive supportive measures as necessary. There is no known specific antidote for apremilast overdose. Actual treatment should depend on the severity of the clinical situation and the judgment and experience of the treating physician.

Overdose for this protocol, on a per dose basis, is defined as ingestion of any more than the amount prescribed of apremilast (or matching placebo) tablets in any 24 hour period whether by accident or intentionally.

IX. PATIENT'S WITHDRAWAL

The patient may withdraw from the study or withdrawn due to the many reasons:

- Loss to follow-up

- Adverse Event
- Non-Compliance
- Minimal/no therapeutic effect.
- Withdrawal of the patient by the investigator.
- Other reasons

Efforts should be made to follow-up patients with adverse events to know the final outcome of the event.

The patient and/or investigator, both have the right to terminate the patient's participation in the study. The reason for termination/withdrawal will be documented.

X. DATA MANAGEMENT

All data must be entered into the clinical data management system before initiating treatment. Electronic case report form (CRF) will be used for the collection of all study data entry at the clinical trial site. The PI will enter the data. All requested information must be entered in the CRF in a timely manner and the CRF for each visit must be completed during the visit. The completed CRF must be reviewed, signed and dated by the PI as well as any missing data should be recorded. Files containing electronic data will be password protected and encrypted and will be closed when computers are left unattended. Contact lists, recruitment records, or other documents that contain Protected Personally Identifiable Information (PPII) will be stored securely in locked cabinets or rooms and access to key codes will be limited.

XI. PUBLICATION PLAN

1.Target Journal: JAAD

2. If Other Specify: JAMA

3. Date of Planned manuscript: September 2019

XII. SUPPORT REQUESTED FROM CELEGENE RESOURCES

1. Requesting Study Drug? Yes

2. Requesting Study funding? Yes

3. Support Requested from other companies? No

4. Non-Celegene Support Sources: None

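### Section VI does not say which CDASI scores LOCF may carry, so an early stopper's off-drug score could become the month-3 or month-6 value

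*Combined protocol and SAP*

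**What the plan says.** Section VI (Statistical Plan) lists descriptive proportions for response at months 1, 3 and 6 and for durability, then adds one sentence: "Missing data will be handled using the last observation carried forward approach (LOCF". It does not limit the rule to on-drug scores or to particular visits, and it does not say how a patient who stops apremilast early is classified.

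The primary objective (Section IV.1) is "To determine the overall response rate (ORR) of apremilast in cutaneous disease of patients with recalcitrant dermatomyositis at 3 months". The responder rule there includes "Partial response is defined by a decrease of CDASI score of at least 4 points", and change is taken from baseline. The durability objective (Section IV.2) is "To determine the durability of responses for up to 6 months on apremilast for responders at 3 months". Complete durability means that the month-6 score minus the month-3 score is zero or below.

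Section IV.2 also has a separate post-treatment objective: "Patient will be assessed 1 month after discontinuing apremilast (follow up visit) to assess change in response post discontinuation of apremilast". At that visit, "Patients will be examined and, CDASI, MMT-8 and DLQI will be performed". The Schedule of Events marks CDASI under the follow-up column. Neither place restricts the visit to patients who complete six months.

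Early stopping is foreseen. The Brief Study Synopsis says "Treatment will be discontinued at disease progression or unacceptable adverse events", and Section IX lists "Minimal/no therapeutic effect" among the reasons for withdrawal. No assessment at the moment of stopping is scheduled.

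**The concern.** The follow-up CDASI exists to show what happens once the drug is withdrawn. The response and durability endpoints are meant to describe the drug while it is taken, explicitly so for durability. If LOCF may draw on any score, one off-drug measurement could serve both purposes for the same patient.

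The error has no fixed direction. A patient doing well on drug may worsen after stopping and be counted a non-responder. A patient with little change on drug may have a lower score a month later, for whatever reason, and be counted a responder. The result could not be called conservative, and in a study this small one such patient visibly changes the headline figure. If the choice of score is left to the analysis stage, it could be made with the results in view.

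**Working it through.** The plan gives no sample-size, power or dropout figure for the clinical endpoints, so there is nothing of its own to reproduce. The check is on timing and classification.

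**Inputs**
- Scheduled CDASI at months 0, 1, 3 and 6 (Brief Study Synopsis; Schedule of Events).
- Off-drug CDASI one month after stopping (Section IV.2; Schedule of Events).
- Partial response: score minus baseline of −4 or lower (Section IV.1).
- Complete durability: month 6 minus month 3 ≤ 0 (Section IV.2).
- Planned enrolment: 10 (Section V).

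**Step 1: which score LOCF selects.** Let a patient stop at month s and attend no later scheduled visit except the follow-up at s + 1. LOCF takes the latest score at or before the target visit.
- Month 3 is off drug when s + 1 ≤ 3, so s ≤ 2.
- Month 6 is off drug when s + 1 ≤ 6, so s ≤ 5. This includes stops before month 3.

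| Stop (month) | Month-3 value, all scores | Month-6 value, all scores | Month-3 value, on-drug only | Month-6 value, on-drug only |
|---|---|---|---|---|
| 1 | month 2, off | month 2, off | month 1 | month 1 |
| 2 | month 3, off | month 3, off | month 1 | month 1 |
| 2.5 | month 1, on | month 3.5, off | month 1 | month 1 |
| 3 | month 3, on | month 4, off | month 3 | month 3 |
| 5 | month 3, on | month 6, off | month 3 | month 3 |
| 5.5 | month 3, on | month 3, on | month 3 | month 3 |

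For a stop at month 2, the follow-up visit falls on month 3 itself; for a stop at month 5, it falls on month 6. In those cases the off-drug score is observed at the target visit rather than carried to it.

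If stop times were spread evenly (an assumption), 2/3 = 67% of stops before month 3 would give an off-drug month-3 value. Likewise 5/6 = 83% of stops before month 6 would give an off-drug month-6 value.

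**Step 2: effect on classification (assumed scores).**
- Baseline 20, month 1 on drug 14, follow-up off drug 19. On-drug change is 14 − 20 = −6, a response. Off-drug change is 19 − 20 = −1, no response.
- With 14 and 19 exchanged, the on-drug score gives no response and the off-drug score gives a response.
- In that second case, with a stop at month 1, the off-drug score of 14 from month 2 fills both month 3 and month 6. The difference is 14 − 14 = 0. The patient counts as a month-3 responder with complete durability after five of the six months off drug.

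**Step 3: on-drug scores only.** A month-3 responder who stops at month 3 has that score carried to month 6. The difference is 0 whatever happens next, so complete durability is automatic. Similarly, a patient who stops at month 1 with a response at that visit stays a responder at months 3 and 6.

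**Step 4: size.** One patient is 1/10 = 10 percentage points of the response rate. In the durability denominator, with 5 month-3 responders (assumed), one patient is 1/5 = 20 points. The chance of at least one early stopper among 10 is 1 − (1 − p)^10. For assumed p of 10%, 20% and 30%, this is 65%, 89% and 97%. Not every stopper would change class.

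**The case against.** The strongest reply is that the plan never says the follow-up score is to be carried. Section IV.1 names months 0, 1 and 3 for the response rate, durability is built from months 3 and 6, and the follow-up visit has its own stated purpose. An analyst could reasonably carry scores only within the named visits. That stands: the off-drug substitution is a possible result of the rule, not a certain one. But the LOCF sentence does not refer to those visit lists, and the narrower reading leads to the durability problem in Step 3. Neither reading classifies early stoppers soundly.

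Other limits also stand. Patients lost to follow-up may have no follow-up visit. The plan does not say that patients who stop the drug miss months 3 and 6; if they attend, LOCF is not used, although the observed score is still off drug. The study is descriptive with a single group, so no hypothesis test is at risk.

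A reader might go further than the documents allow in three ways.
- One might infer that a patient stopped for progression needs only a 4-point improvement to count as a responder. Response is measured from baseline. If the 4-point rise in the progression definition is also from baseline (no reference point is given), the score must fall 4 + 4 = 8 points. Nor do the documents describe any change of other treatment after stopping.
- One might cite a month-3 responder who stops for an adverse event and then flares as wrongly counted as a loss. The rule proposed below also counts that patient as not durable, so the case does not distinguish the approaches.
- One might read the on-treatment wording into the primary objective. It appears only in the durability objective; the primary objective speaks of the response rate of apremilast.

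**Conclusion.** The point holds as a gap in the stated rule. Section VI leaves open which scores LOCF may use, and both natural readings can misclassify patients who stop early. If all scores are eligible, an off-drug CDASI could supply the month-3 value for stops up to about month 2 and the month-6 value for stops up to about month 5. If only on-drug scores are eligible, a month-3 responder who stops is durable by construction.

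Each reclassified patient is worth 10 percentage points of the response rate, and more in the smaller durability denominator. How many patients would be affected cannot be derived from the documents and could be none. The timing rests on the follow-up visit taking place one month after the last dose and on no later scheduled visit being attended. The documents do not support saying that every early stopper will be misclassified, or that the bias runs in one direction.

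**What to change.** Amend Section VI as follows.
- Do not use CDASI scores taken after the last dose, whether observed or carried forward, for month-3 response, month-6 response or durability.
- Count a patient who stops apremilast before month 3 as a non-responder for the primary response rate.
- Count a patient who stops before month 6 as a non-responder at month 6.
- Count a month-3 responder who stops before month 6 as not durable on apremilast.
- Report off-drug scores only under the post-discontinuation objective.
- If wanted, show the result under the present LOCF sentence as a sensitivity analysis, stating which scores were carried.

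Non-responder counting is one accepted strategy among several. It is proposed here because it settles all three endpoints with one rule that can be fixed in advance. For 6-month response, which the plan assesses in all patients without on-treatment wording, excluding off-drug scores is a choice and should be stated as one.

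The cost is wording only, with no new visits or data. The downside is that response and durability rates may be lower, by up to 10 points of response rate per affected patient.

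### Under the unqualified LOCF rule, a month-1 responder with no later CDASI counts as a responder in the 3-month primary ORR, and possibly as a complete durable response at month 6

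*Combined protocol and SAP*

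**What the plan says.** Section IV.1 sets the primary objective: "To determine the overall response rate (ORR) of apremilast in cutaneous disease of patients with recalcitrant dermatomyositis at 3 months". On timing it says "The ORR will be measured using the Cutaneous Dermatomyositis Activity and Severity Index (CDASI) at months 0, 1, and 3", and on the threshold "Partial response is defined by a decrease of CDASI score of at least 4 points". A complete response is a score of zero.

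Section V gives the number "of Patients Expected to Enroll: 10". Section VI opens with "Results of the study will be analyzed using descriptive statistics", lists the proportions to be reported, and adds "Missing data will be handled using the last observation carried forward approach (LOCF". That sentence exempts no endpoint and no reason for missingness. The documents contain no non-responder rule, no defined denominator or analysis set for the ORR, and no sensitivity analysis.

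Patients can leave before month 3. The Brief Study Synopsis (item 7) says "Treatment will be discontinued at disease progression or unacceptable adverse events". Section IX begins "The patient may withdraw from the study or withdrawn due to the many reasons" and lists loss to follow-up, adverse events, non-compliance and lack of effect among them.

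Two further provisions matter. Section IV.2 and the Schedule of Events plan a CDASI one month after apremilast is stopped. Section IV.2 also defines complete durability, among 3-month responders, as a month-6 score no higher than the month-3 score.

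**The concern.** The endpoint asks whether the patient is in response at 3 months. LOCF can answer it with a score taken two months earlier, from a patient who was not seen again. In a single-group study there is no comparator in which the same substitution would occur. With 10 patients, one substitution visibly changes the headline proportion.

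The durability analysis builds on the same status. A patient last seen at month 1 could enter the set of 3-month responders and then be recorded as fully durable, with no CDASI observed at month 3 or month 6.

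For patients who stop the drug and attend the post-discontinuation visit, the plan does not say whether that off-drug score is the one carried forward. Two analysts could follow Section VI faithfully and report different ORRs.

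**Working it through.** The plan gives no figure to reproduce: the sample size of 10 is stated without a derivation, and no response or dropout rate is assumed.

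**Step 1: which score is carried to month 3**

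| Patient | Score carried to month 3 under Section VI | Status at month 3 |
|---|---|---|
| Fall of at least 4 points at month 1, no later CDASI | Month 1 | Responder |
| Fall of less than 4 points (and score not zero) at month 1, no later CDASI | Month 1 | Non-responder |
| Leaves before month 1, no later CDASI | Baseline | Non-responder |
| Stops drug after month 1, post-discontinuation CDASI taken before month 3, no month-3 CDASI | Not settled: month 1 or the off-drug score | Depends on the reading |

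Only the first row follows from the text without a further assumption.

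**Step 2: effect on the ORR**

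Let r be the observed month-3 responders and k the month-1 responders with no later CDASI.

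- ORR under LOCF = (r + k)/10.
- ORR under non-responder imputation = r/10.
- Observed-case ORR = r/(10 − k), if no one else is missing.
- LOCF minus non-responder imputation = k/10, or 10 points per patient.

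Illustration with r = 4, with exact (Clopper-Pearson) 95% intervals added here, since the plan specifies none:

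| k | LOCF | Non-responder imputation | Observed case |
|---|---|---|---|
| 1 | 50% (18.7-81.3) | 40% (12.2-73.8) | 4/9 = 44.4% |
| 2 | 60% (26.2-87.8) | 40% (12.2-73.8) | 4/8 = 50.0% |

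**Step 3: how likely this is**

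Let d be the probability that a patient is lost between months 1 and 3 with no later CDASI, and q the probability of month-1 response among those lost. Both are assumptions. Patients are treated as independent.

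- Expected difference in ORR = d × q.
- Chance of at least one such patient = 1 − (1 − d × q)^10.

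| d | q = 20% | q = 40% | q = 60% |
|---|---|---|---|
| 10% | 2 points; 18% | 4 points; 34% | 6 points; 46% |
| 20% | 4 points; 34% | 8 points; 57% | 12 points; 72% |
| 30% | 6 points; 46% | 12 points; 72% | 18 points; 86% |

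For example, 1 − 0.98^10 = 0.18 and 1 − 0.82^10 = 0.86.

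**Step 4: durability**

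If the month-1 score fills both month 3 and month 6, the month-6 minus month-3 difference is x − x = 0, which satisfies the definition of complete durability in Section IV.2.

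**The case against.** A reader might infer that every patient who improves at month 1 and then stops for intolerance is counted on the month-1 score. The documents do not support that. Such a patient is due a CDASI one month after stopping. If that visit is attended before month 3, a literal last observation is the off-drug score. Nor do the documents say that patients who stop the drug skip the month-3 visit; if they attend, nothing is missing. The result is certain only for patients with no CDASI after month 1.

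A reader might also take the difference as proven inflation. It is not. LOCF cannot give a lower ORR than non-responder imputation over the same patients, but that follows from how the two rules are built. The difference is bias only to the extent that these patients would have lost response by month 3, which is unknown for someone lost for unrelated reasons. Section IV.2 itself allows for delayed response, so a month-1 non-responder who leaves may be understated by both rules.

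The assumed rates may also be high. The protocol describes gastrointestinal effects as transient, and leaving for progression or lack of effect would mostly select non-responders. At the lowest setting in the table, the chance that no patient is affected is 0.98^10 = 82%.

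Finally, the ORR analysis is descriptive, with no null rate or success threshold, and the intervals at n = 10 are far wider than a one-patient shift. Separate reporting of month-1 response also shows early response.

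All of this limits size and severity. None of it removes the core point: the written rule can credit a 3-month response with no 3-month observation, and reporting month 1 separately does not correct the month-3 figure.

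**Conclusion.** The point holds for patients in response at month 1 with no later CDASI: those lost to follow-up, or those who stop early and do not attend the post-discontinuation visit. Each adds 10 percentage points to the primary ORR relative to non-responder imputation, and each can also be credited with complete durability if the same score fills month 6. For patients who stop and do attend that visit, the plan is silent on which score counts.

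Under the assumed ranges (loss 10-30%, month-1 response among those lost 20-60%), the two rules differ by 2-18 points in expectation, with an 18-86% chance of at least one affected patient. These figures rest wholly on assumed rates and describe a gap between rules.

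This should be fixed. It is not critical, because no test, error rate or decision rule depends on the ORR. But the point estimate is the main result, and the repair is cheap.

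**What to change.** In Section VI, for the binary CDASI response endpoints, replace LOCF with:

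> *A treated patient who has stopped apremilast or left the study before a visit, or who otherwise has no on-treatment CDASI for that visit, is a non-responder at that visit. The denominator is all patients who took at least one dose. Off-drug follow-up scores do not fill scheduled visits.*

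Report LOCF and observed-case results as labelled sensitivity analyses. List separately any patient who stayed on the drug and missed only that visit. The rule also closes the durability route, because a patient without a month-3 on-treatment score no longer enters the set of 3-month responders.

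Settle this before any response data are examined, including the interim analysis that Section V plans.

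The cost is a short text change, with no new visits, data or patients. There are three downsides:

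- Over the same patients, the reported ORR can only stay the same or fall.
- An isolated missed visit by a patient still on the drug is counted conservatively, which is why the separate listing is needed.
- A patient who has stopped but attends month 3 off the drug is counted as a non-responder. That is a deliberate choice to measure response while on apremilast, and the plan should say so.
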